8.3.1 Dose modifications

Based on clinical judgement, it may be decided to extend the dosing period for some participants. For example, a change from 2.5mg BID for 7 days to 2.5mg BID for up to 14 days. In particular, if participants have significant benefits from therapy, but show relapses of the COVID-19 inflammatory state (rising CRP and increasing oxygen requirements in the absence of bacterial infection), on completing 7 days of treatment, then the medical team have the choice of reinstating dornase alfa treatment for up to 7 further days (14 days in total) at 2.5mg BID. Blood sampling will continue until the last day of dosing with dornase alfa.

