8.8 Discontinuation/withdrawal of participants

In consenting to participate in the trial, participants are consenting to trial treatment, assessments, follow-up and data collection.

Discontinuation of trial treatment for clinical reasons

A participant may be withdrawn from trial treatment whenever continued participation is no longer in the participant's best interests, but the reasons for doing so must be recorded. Reasons for discontinuing treatment may include:

- Alternative clinical diagnosis emerges (no longer considered to have primary COVID-19 lung disease).
- Disease progression whilst on therapy.
- Unacceptable toxicity.
- Intercurrent illness which prevents further treatment.
- Patients withdrawing consent to further trial treatment.
- Any alterations in the participant's condition which justifies the discontinuation of treatment in the Cl's or designee's opinion.
- Persistent non-compliance to protocol requirements.
- Participant is put on end of life pathway and dies prior to dosing.

The decision to withdraw a participant from treatment must be recorded in the CRF and medical notes, and the sponsor when required should be notified in writing.

Participant withdrawal from trial treatment or follow-up

If a participant expresses their wish to withdraw from trial treatment or follow-up, sites should explain the importance of remaining on trial follow-up and seek permission to allow use of routine follow-up data to be used for trial purposes. The importance of safety follow-up should be emphasised to the participant in the Participant Information Sheet.

The decision of the participant to withdraw from treatment or follow-up must be recorded in the CRF and medical notes.

The participant may withhold their reason for withdrawal however, if the participant gives a reason for their withdrawal, this should be recorded.

Withdrawal of consent to data collection

If a participant explicitly states that they do not wish to contribute further data to the trial their decision will be respected and recorded in the CRF and medical notes.

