9.4 Procedures for recording and reporting Serious Adverse Events

All serious adverse events (SAEs/SARs/SUSARs) will be recorded in the medical records in the first instance. Serious Adverse Events (SAEs) related to COVID-19 will not be collected in the CRFs or reported to Sponsor for this trial.

All other SAEs will be recorded in the CRF, and the sponsor's SAE Recording Log and SAE Reporting Form.

All SAEs will be recorded from randomisation until 24h after last study dose.

All SAEs (except Covid-19 related SAEs specified in section as not requiring reporting to the Sponsor), must be recorded on a serious adverse event (SAE) Reporting Form. The CI/PI or designated individual will complete the sponsor's SAE form and email to the Sponsor at [contact], within 24 h of his/her becoming aware of the event. The Chief or Principal Investigator or designee will respond to any SAE queries raised by the sponsor as soon as possible.

Completed SAE forms must be sent within 24 hours of becoming aware of the event to the Sponsor Email forms to [contact]

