### 4. PLANNED ANALYSES

There are two planned analyses, an interim analysis after 12 randomised individuals have completed Day7 follow-up and the final analysis, once all randomised individuals have completed follow-up (which is the minimum of discharge, death or 35 days after randomisation). At the interim analysis, only the primary endpoint and safety data will be examined, and no secondary or exploratory endpoints. A promising zones approach [1] (see Section 12 for details) will be followed at the interim analysis stage to identify the conditional power and make a decision as to whether to continue enrolment up to the planned 40 individuals randomised, or whether to increase the planned sample size up to a maximum of 48 randomised individuals. See Section 12 for details.

After the final randomised participant has completed follow-up, a more complete analysis will be undertaken, including examination of endpoints relating to the primary, secondary and exploratory objectives. A full safety analysis will also be carried out at this stage.

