#### 11.4 Safety analyses

Safety of dornase alfa will be assessed by comparisons of adverse events (AEs), serious adverse events (SAEs), treatment-emergent adverse events (TEAEs) and deaths. The safety population is defined in Section 6.4.

All AEs will be summarized by BAC + dornase alfa/BAC only. A TEAE is an AE that starts or worsens at any time after initiation of study drug on Day1 through to end of follow-up.

For SAEs occurring in  $\geq$ 5% of individuals, follow-up-adjusted event rates based on events by randomised arm will be provided. The rates will be calculated as the total number of events in the randomised arm divided by the total sum of days follow-up in that randomisation arm, multiplied by 365.25, to give the expected number of events per patient year.

Listings of all TEAEs and SAEs will be provided.

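### Protocol 9.4 stops SAE recording 24 hours after the last dose and gives BAC no end date, but the SAP 11.4 SAE rate counts all follow-up days

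*SAP*

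**What the plan says.** **Recording window.** Protocol 9.4: "All SAEs will be recorded from randomisation until 24h after last study dose". Dosing is Day 1 to Day 7 (Protocol 5.1). Protocol 8.3.1 also allows the medical team the option of "reinstating dornase alfa treatment for up to 7 further days (14 days in total"). Treatment may stop early, for reasons that include "Unacceptable toxicity" (Protocol 8.8).

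**Rate.** SAP 11.4 takes SAEs occurring in at least 5% of individuals, counts events by randomised arm, "divided by the total sum of days follow-up in that randomisation arm", and multiplies by 365.25. SAP section 4 defines follow-up, "which is the minimum of discharge, death or 35 days after randomisation". The safety population (SAP 6.4) contains both randomised arms.

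**Sections that point to a longer window.**
- Protocol 8.4.1 lists a daily AE review among the follow-up assessments.
- Appendix 1 marks AE review at the final visit (discharge or Day 35), and its footnote 12 has AEs recorded every day.
- Protocol 8.8: "The importance of safety follow-up should be emphasised to the participant in the Participant Information Sheet".
- SAP 11.4 defines a TEAE as an AE that "starts or worsens at any time after initiation of study drug on Day1 through to end of follow-up".

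**What is not collected.** Protocol 9.2, 9.4 and 9.5 keep a list of anticipated COVID-19-related events, among them worsening respiratory failure, organ failure and death, out of the CRF and the SAE log. The exception is an event whose frequency or severity does not fit COVID-19.

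**The concern.** A person-time rate is interpretable only if events can be recorded on every day counted in its denominator. Read together, Protocol 9.4 and SAP 11.4 break that rule: the numerator closes about a day after dosing ends, while the denominator runs on to discharge, death or Day 35. The sections that continue AE review would remove the mismatch, since an SAE is defined in Protocol 9.1 as a kind of AE, but neither document says which of them governs SAE recording.

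The BAC arm adds a second gap. Its patients receive no study drug, so the 9.4 window has a start but no end for one of the two arms being compared. The AE definition (Protocol 9.1) and the TEAE start (SAP 11.4) are also worded for treated patients, although collection in BAC is clearly intended: the safety population includes them, and Protocol 11.4 tabulates AEs by treatment.

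At stake are the level of the reported SAE rate, the completeness of SAE counts and listings, and possibly the comparison between arms. This is a new population for the drug, with sentinel dosing for the first three participants (Protocol 3.1), so the safety tables should mean what they say.

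**Working it through.** The plan states no SAE rate or expected SAE count, so there is no figure to reproduce. The check is of the formula.

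**Inputs**
- Window W: 7 dosing days + 1 = 8 days (Protocol 5.1, 9.4). With 14 dosing days, W = 15 (Protocol 8.3.1).
- Follow-up d: at most 35 days (SAP section 4). Length of stay is not given, so a range is assumed.
- Shape of the SAE hazard: not given, so two shapes are assumed: constant, and halving every 7 days.

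**Formula.** Let H(t) be the expected number of reportable SAEs per patient by day t. The rate over follow-up is H(d)/d. With recording stopped at W, the SAP formula returns H(W)/d. The understatement factor is H(d)/H(W) for d > W, and 1 otherwise.

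- Constant hazard: d/8.
- Halving hazard, k = ln2/7: (1 − exp(−kd)) / (1 − exp(−8k)), where 1 − exp(−8k) = 0.547.

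| Follow-up d (days) | Constant | Halving every 7 days |
|---|---|---|
| 8 or less | 1.00 | 1.00 |
| 10 | 10/8 = 1.25 | 0.629/0.547 = 1.15 |
| 20 | 20/8 = 2.50 | 0.862/0.547 = 1.58 |
| 35 | 35/8 = 4.38 | 0.969/0.547 = 1.77 |

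**Mixed lengths of stay.** If half the arm leaves at Day 8 and half stays 20 days (constant hazard), mean follow-up is 14 days against 8 recorded: 14/8 = 1.75.

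**Extended dosing.** With W = 15 and d = 35 (constant hazard): 35/15 = 2.33.

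**Early stop.** A patient who stops after 3 dosing days (W = 4) and is followed for 20 has a factor of 20/4 = 5.0 (constant) or 0.862/0.327 = 2.6 (halving).

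**Between arms.** Equal true rates, 20 days' follow-up in both arms:

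| How SAEs are collected | Apparent dornase alfa:BAC rate ratio |
|---|---|
| Dornase alfa to Day 8, BAC to Day 20 | 8/20 = 0.40 (constant); 0.547/0.862 = 0.63 (halving) |
| Both arms to Day 8 | (8/20)/(8/20) = 1.0 |
| Both arms to final visit | 1.0 |

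**Threshold.** Across the safety population, 5% means 2 of 40 participants. At 48 it means 3, since 2/48 = 4.2% and 3/48 = 6.3%. One unrecorded SAE can therefore decide whether a rate is shown.

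**The case against.** The strongest reply is that little may be left to dilute. Listed COVID-19-related SAEs, including death, stay out of the CRF whatever the window, so the factors apply only to the remaining reportable SAEs. After that exclusion, few event types may reach 5% and the rate may never be produced. Deaths are captured separately for survival to Day 35 (SAP 2.2.2 and 11.2). Follow-up ends at discharge, so a patient discharged by Day 8 contributes no unrecorded days. If no reportable SAE can occur after the window, the factor is 1. All of this stands. It limits the size and the grade but does not reconcile the sections.

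Three stronger readings are tempting and are not supported.
- *The comparison is biased towards dornase alfa.* The ratio of 0.40 or 0.63 requires only the dornase alfa arm to be cut, and no section prescribes that. The blood-volume table in Protocol 8.5 has a 7-day BAC row, which hints at a parallel nominal course without defining a last dose. If both arms are cut at about Day 8 with similar follow-up, the dilution largely cancels.
- *Early stopping hides the gravest events.* Much of what follows disease progression is on the excluded list under any window. The early-stop example matters only for reportable SAEs.
- *The patient described by "Participant is put on end of life pathway and dies prior to dosing" is a case of dilution.* Such a patient has no last dose, but follow-up ends at death, so no unrecorded person-time is added.

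On timing, SAP version 1.6 is dated August 2021, and its change log drops analyses because the available data were insufficient. Data may already have been in hand, so a change to collection could come late. The fix needs a fallback for that.

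**Conclusion.** The inconsistency is real. Followed as written, Protocol 9.4 and SAP 11.4 give an SAE rate that is too low for patients followed past the recording window, leave later SAEs out of counts and listings, and leave the BAC arm without an end of SAE recording.

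With 7-day dosing the understatement is none if follow-up ends by Day 8. At 10, 20 and 35 days it is 1.25-, 2.5- and 4.4-fold under a constant hazard, or 1.15-, 1.58- and 1.77-fold if the hazard halves weekly. The 35-day figures are the extreme, and lengths of stay and hazard shapes are assumptions. The effect on the arm comparison is undetermined: the ratio could be as low as 0.40 in the one-sided 20-day scenario, or about 1.0 if both arms are handled alike. If staff collect SAEs to the final visit in both arms, there is no window error at all.

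The rate is descriptive, with about 10 BAC patients and no formal test, and efficacy is unaffected. Minor to should-fix.

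**What to change.** 1. Reconcile Protocol 9.4 with 8.4.1, Appendix 1 and SAP 11.4. State one SAE window for both arms, from randomisation/Day 1 to end of follow-up (discharge, death or Day 35). The SAP 11.4 formula then stands unchanged. AEs are already assessed daily and written in the medical records (Protocol 9.2), so reportable SAEs after the present cut-off can be entered from the notes.
2. If collection can no longer be changed, apply one common cut-off from randomisation/Day 1 to events and person-days in both arms, no later than the day to which SAEs were actually recorded. End it earlier at discharge, death or withdrawal, and list later events separately. Day 15 should not be assumed to cover extended dosing: Protocol 8.3.1 describes reinstatement after a relapse, so a gap could push the last dose plus 24 hours beyond it.
3. In either case, state beside the rate that listed COVID-19-related SAEs are excluded from the numerator.
4. Word the AE definition (Protocol 9.1) and the TEAE definition (SAP 11.4) from randomisation/Day 1, so that both apply to BAC.

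The cost is a short protocol amendment, small SAP edits and some retrospective entry from the notes. The fallback in item 2 also needs a minor change to the person-time derivation.

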#### **12. INTERIM ANALYSIS**

At the interim analysis, baseline demographics, subject disposition and primary endpoint analyses will be carried out. This will occur after the first 12 randomised individuals have completed Day7 follow-up.

A sample size re-estimation will be performed based on a promising zones approach [1].

At the interim stage, the following individuals will be included:

- approximately 9 individuals randomised to BAC + dornase alfa
- approximately 3 individuals randomised to BAC only
- approximately 18 individuals (2 × the number of individuals randomised to BAC + dornase alfa) included from the matched historical control cohorts

This gives a total of approximately 30 individuals included in the analysis. However, if there are insufficient HC data available at the interim analysis to perform propensity score matching (less than 3 × the number of individuals randomised to dornase-alfa), all HCs will be included in the interim analysis.

Prior to an interim analysis sample size re-estimation, the planned sample size at the final analysis is to include:

• 30 individuals randomised to BAC + dornase alfa

#### **Exploristics Limited**

## Identifier: EXP20012 Clinical Study Identifier: 132333

- 10 individuals randomised to BAC only
- 60 individuals (2 × the number of individuals randomised to BAC + dornase alfa) included from the matched historical control cohorts

Therefore the planned sample size is 100 individuals.

However, at the interim analysis, a sample size re-estimation will be carried out, and the overall sample size could be increased to a maximum of:

- 36 individuals randomised to BAC + dornase alfa
- 12 individuals randomised to BAC only
- 72 individuals (2 × the number of individuals randomised to BAC + dornase alfa) included from the matched historical control cohorts

Giving a maximum permitted sample size of 120 individuals.

A decision rule for whether to increase the number of individuals randomised into the trial will be derived using a promising zones approach [1]. This approach calculates the power at the interim analysis, conditional on the interim standardised treatment effect size, termed the conditional power. The conditional power at the interim stage will fall into one of three possible zones, a futility zone, a promising zone or a favourable zone.

- If the conditional power is below 0.46 it will be considered to fall into the futility zone. If the conditional power is in the futility zone at the interim analysis, it is unlikely that the final analysis will produce a p-value of <0.05 for the treatment effect, even if the sample size were increased to the maximum permitted sample size of 48 individuals randomised. Therefore, if the conditional power falls in the futility zone at the interim, recruitment will continue as planned to 40 randomised individuals and a final analysis will be performed as originally planned.

- If the conditional power is between 0.46 and 0.8, it will be considered to fall into the promising zone. In this zone, there is less than the 80% power that the study was powered for originally, but if the sample size were to be increased to somewhere between 40 and 48 randomised individuals, the power could be increased to close to 80%, and there would be an increased probability of observing a p-value of <0.05 for the treatment effect at the final analysis.
- If the conditional power is above 0.8, the conditional power will fall into the favourable zone. In this zone, there is more than the 80% power that the study was powered for originally. Therefore, recruitment will be continued to the planed 40 randomised individuals without a change to the planned sample size. There will be no decrease in planned sample size since the treatment effect at the interim analysis could be an over-estimate by chance.

# **Exploristics Limited**

Identifier: EXP20012 Clinical Study Identifier: 132333

## 13. ATTACHMENTS

# 13.1 Table of Contents for Data Display Specifications

Final analysis

See TFLs\_v1.6\_clean.docx for final set of Tables, Figures and Listings.
